7.1.4 Conservative Treatment Group 3 Months (± 14 days), or VA3

Patients randomized to the conservative arm will be evaluated with VASPI, ODI, SF-36 questionnaires as well as complete all required additional assessments as outlined in Appendix A during the 3 months visit. Patients will be evaluated for deteriorating or improving conditions relative to enrollment. Subjects who have experienced a significant decline in condition defined as a 10% increase in pain by VASPI, or a 9-point increase in ODI will be offered the allograft treatment as a crossover. If the subject does not meet the aforementioned changes in ODI or VASPI, or is considering withdrawal, they may also be offered the allograft treatment by physician discretion if condition has significantly declined. Subjects that crossover do not have to re-consent. The crossover allograft treatment can occur at any time period after the 3-month follow-up visit. To administer the crossover allograft treatment, a new visit will be scheduled and this visit will be considered as the new Active Phase Day 0. In addition to the 3 months follow-up visit assessments, these crossover subjects will receive a MRI and X-ray prior to the allograft treatment. All assessments done at this 3 months follow-up visit will be considered as the new baseline assessments. These crossover subjects will receive follow-up visits at 6 months and 12 months after allograft treatment. Crossover subjects will not be replaced by enrolling new patients in the conservative care treatment group.

7.1.5 Active Phase Month 6 (± 30 days) or VA4:

All randomized subjects will return to the clinic 6 months (± 30 days) subsequent to treatment for all safety and efficacy assessments as outlined in Appendix A. ODI, VASPI, and SF-36 questionnaires will be completed by the subject, and assisted by physician or physician designee. All subjects (excluding conservative care crossover subjects) will be randomized to include MRI at 6-month (MRI or no MRI, ratio 1:1) follow-up in addition to all other assessments. This randomization is performed to assess whether predictability at 6 months indicates performance at 12 months. The conservative care subjects that crossover to the allograft treatment group will all receive an MRI at 6-month follow-up after allograft treatment. All subjects will receive an X-ray at the 6-month follow-up visit. Additionally, a review of resource utilization since the Day 0 visit will be completed.

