8.5 Assessments

- Informed Consent will be obtained between Screening Day -14 and Active Day 0, prior to any study procedures being performed. The addendum for optional long term follow up will be collected before procedure and questionnaires are performed.
- An assessment of eligibility using the inclusion and exclusion criteria will be conducted starting at Day -14 of the Screening Phase. Prior to randomization at Day 0 of the Screening Phase, eligible subjects must meet all inclusion criteria and no exclusion criteria for the Active Phase. This will also be assessed after the ICF addendum for long term follow up is collected to determine if the subject is still eligible.
- Medical History and Patient Demographics will be recorded during the Screening Phase.
- An abbreviated Physical Examination will be done in the Screening Phase within the 2 weeks prior to transplant, as well as at Month 6, and 12, and at 3 months for the subjects randomized to continue conservative care. This will be done for subjects completing the placebo crossover injection as well.
- Resource utilization data (lost time from work, number and kind of previous surgeries, duration of complaints (preoperatively), duration of rehabilitation, complications, additional physician visits, etc.), will be obtained during the Screening Phase as a baseline to similar data obtained during the Active Phase at Months 6, and 12. This will also be collected during the long term follow up visits of 24 and 36 months.
- Physicians clinical assessments will be collected in the Screening and in the 2 weeks prior to transplant, and in the Active Phase at Months 6, and 12, and in the conservative

CONFIDENTIAL	Clinical Protocol	DATE	Р	age
		9Dec2019		
	mented Disc Regeneration in the $\underline{\mathbf{T}}$ reatment of th or without Intervertebral Disc Herniation –	WRITER TG, DB, PW	NO. 37	REV 6

- care patients at 3, 6, and 12 months. A neurological exam will be completed before placebo crossover additionally.
- Patient self-assessments including VASPI, ODI, and SF-36 will be collected at every scheduled clinic visit. VASPI, ODI, and SF-36 will be collected in person at 24 months and at the 36 month interval, these questionnaires can be performed over the phone during optional long term follow up.

CONFIDENTIAL	Clinical Protocol	DATE	Р	age
		9Dec2019		

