9.3 Secondary Endpoints

Secondary parameters of efficacy will include the ODI, the SF-36, and the VASPI following treatment. Structural outcomes will be assessed using X-ray and MRI measurements at the same time points. Safety will be assessed by the incidence and severity of AEs and clinically important changes in laboratory tests.

A correlation of the clinical results (scores and scales) and the morphological results (X-ray, MRI) will be evaluated. All additional efficacy and safety data will be analyzed descriptively.

The effect supplemental allograft transplant on resource utilization, i.e., days off work, subsequent surgeries, other clinic visits will also be measured and compared

CONFIDENTIAL	Clinical Protocol	DATE	Р	age
		9Dec2019		T
TITLE: V iable A llograft S upplemented Disc Regeneration in the T reatment of Patients with Low Back Pain with or without Intervertebral Disc Herniation – VAST-001-017		WRITER TG, DB, PW	NO. 40	REV 6

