APPENDIX A - STUDY SCHEDULE

Visit	VS1 ^a	VA1 ^a	VA2 ^b	VA3 ^c	VA4	VA5	VA6	VA7
Visit Window	Screening (Day -14 to 0)	Day 0	1 month (±3 Days)	3 months (±14 Days)	6 months (± 30 Days)	12 months (+ 30 Days)	24 months (± 3 Months)	36 months (± 3 Months)
Informed Consent	Х						Х	
Eligibility Criteria	Х							
Eligibility Criteria Check		Х					х	
Randomization		Х						
Injection Treatment (Allograft or Saline)		Х					X ^f	
Demographic Data	х							
Medical History	х							
Physical Examination		Х	х	Х	Х	Х	X ^f	
Neurological Examination		Х	Х	X	X	X	Χ ^f	
MRI and X-ray Evaluations	X		X	X ^d	X e	X	X ^f	
Laboratory Investigation	Х		Х	Х	Х	Х	X ^f	
Urine/Pregnancy Test, if applicable		Х						
VASPI Questionnaire	х		х	Х	х	х	х	Х
SF-36 Questionnaire	x		х	х	х	х	х	x
ODI Questionnaire	х		х	Х	х	х	х	х
Resource Utilization	Х				Х	Х	Х	Х
Concomitant Medication	Х	Х	Х	Х	Х	Х	Х	Х
Adverse Events		Х	х	Х	Х	Х	Х	Х

^a VS1 and VA1 may both occur on Day 0.

^b Month 1 Visit (VA2*) to be performed for the first 24 subjects randomized only.

CONFIDENTIAL	Clinical Protocol	DATE 9Dec2019	Pa	ige
	mented Disc Regeneration in the $\underline{\mathbf{T}}$ reatment of th or without Intervertebral Disc Herniation –	WRITER TG, DB, PW	NO. 57	REV 6

^c Subjects randomized to conservative care will be evaluated at 3 months to assure they are not experiencing further debilitating changes. During this visit, subjects may be offered crossover to allograft treatment. To administer the crossover allograft treatment, a new visit will be scheduled and this visit will be considered as the new Active Phase Day 0 (VA1).

^d MRI and X-ray to be done in the event a subject crosses over from conservative care to the Allograft treatment.

^e At the 6-month follow-up visit, subjects will be randomized to receive a MRI, (1:1 ratio). Crossover subjects to allograft treatment will all receive an MRI at the 6 month visit after allograft treatment. All subjects will receive an X-ray at the 6 month follow up visit.

f At the 24-month in-office visit, subjects will first be reevaluated for inclusion/exclusion and fill out VASPI, ODI, SF-36, and Resource Utilization. If eligible for allograft treatment, the PI will perform a neurological exam, physical exam, laboratory investigation, and MRI/X-ray.

[figure not shown]
CONFIDENTIAL	Clinical Protocol DATE		Page	
99111 12 E111111 12		9Dec2019		

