9.2 SECONDARY ENDPOINTS

All secondary variables will be analyzed in an exploratory way, with no adjustment for multiple testing. The secondary endpoints include:

- Improvement in ODI and VASPI at 6 months
- Improvement in ODI, SF-36, and VASPI at 6 and 12 months after treatment
- MRI measurements at 6 and 12 months after treatment
- Adverse Event (AE)/ Serious Adverse Events (SAE) rates after treatment
- Hospitalization rate at 12 months after treatment
- Re-operation rate at 12 months after treatment
- Resource utilization following treatment at 6 and 12 months after treatment
- Changes in laboratory tests

Improvement in ODI, VASPI, and SF-36 will be analyzed similar to the primary endpoint, using the Kruskal-Wallis test to test for an overall difference between the three treatment groups. If the overall test is significant, the Dwass, Steel, Critchlow-Fligner Method will be used to asses all pairwise comparisons.

Adverse event rates, serious adverse events rates, hospitalization rates, and re-operation rate will be summarized by treatment group and compared using the chi-square test of independence or Fisher's exact test, as appropriate.

MRI data will be summarized by treatment group as mean at each timepoint, and mean change from baseline. Analyses will be done focusing on the level treated, but additional analyses will be completed which examine all five levels to see if there are adjacent level effects. Group comparisons will be made using the Krusal-Wallis test. If the overall test is significant, the Dwass, Steel, Critchlow-Fligner Method will be used to assess the pairwise comparisons.

Resource utilization and changes in laboratory tests will be summarized by treatment group.

10 Adverse Events

All adverse events will be coded using the standardized Medical Dictionary for Regulatory Activities (MedDRA) central coding dictionary, version 22.1 or greater.

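### Conservative-care patients who cross over before their original Month 6 visit have no scheduled review of resource use between original Day 0 and crossover

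*Protocol*

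**What the plan says.** Protocol 8.5 says that resource data "will be obtained during the Screening Phase as a baseline to similar data obtained during the Active Phase at Months 6, and 12", with Months 24 and 36 added for the extension. The Resource Utilization row of Appendix A agrees: it is marked at VS1 and VA4 to VA7, and not at VA1 (Day 0), VA2 (Month 1) or VA3 (Month 3). Section 7.1.5 adds for Month 6: "Additionally, a review of resource utilization since the Day 0 visit will be completed". Section 7.1.6 asks for a review through Month 12 and gives no start date.

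For crossovers, section 7.1.4 states: "The crossover allograft treatment can occur at any time period after the 3-month follow-up visit". For the injection, "a new visit will be scheduled and this visit will be considered as the new Active Phase Day 0", and footnote c of Appendix A also labels that visit VA1. Follow-up then runs 6 and 12 months from the allograft. Section 7.1.4 also says: "All assessments done at this 3 months follow-up visit will be considered as the new baseline assessments".

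On use of the data, Protocol 9.3 says that the effect of the transplant "on resource utilization, i.e., days off work, subsequent surgeries, other clinic visits will also be measured and compared". SAP 9.2 says: "Resource utilization and changes in laboratory tests will be summarized by treatment group". SAP section 9 analyses secondary variables in the mITT and PP populations, and SAP 6.2 keeps mITT patients in their randomised group.

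**The concern.** Month 3 is the visit at which crossover is offered and whose assessments become the new baseline, yet resource use is not among those scheduled there. Once Day 0 moves to the crossover visit, the Month 6 review no longer clearly reaches back into the conservative-care period.

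That period is not a random sample of patient time. Crossover is offered after a 10% rise in VASPI, a 9-point rise in ODI, or a decline judged by the physician. Lost work and extra visits are plausibly more frequent at such a time. The Rationale presents economic efficiency as part of the method's aim, so the conservative-care figure is the reference that a reader will look for.

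**Working it through.** The plan states no figure on this point, so there is none to reproduce. The check sets the schedule against the crossover rule and counts uncovered months.

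Inputs:
- Collection points: VS1 and VA4 to VA7 (Appendix A; Protocol 8.5).
- Month 3 window of ±14 days (7.1.4). The earliest crossover is therefore about 3 − 14/30 ≈ 2.5 months after original Day 0.
- Month 6 window of ±30 days (7.1.5). The original Month 6 visit falls at 5 to 7 months.
- Crossover at any time after the Month 3 visit, with no upper limit (7.1.4).
- Conservative-care arm of 40 (Protocol synopsis; SAP section 4).

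Let c be the month of crossover and v the month of the original Month 6 visit, both counted from original Day 0.

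**Literal reading** (Day 0 means the crossover visit, and no form is taken at VA3 or at the new VA1):
- Crossover before the original Month 6 visit: uncovered time = c. This runs from 2.5 months at the earliest crossover to about 7 months for a crossover just before a Month 6 visit held at the end of its window. A crossover at Month 3 leaves 3 months uncovered.
- Crossover after that visit: uncovered time = c − v. For c = 9 this is 9 − 7 = 2 months to 9 − 5 = 4 months.

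**Other readings:** if the look-back runs to original Day 0, or if a form at the new VA1 reaches back to it, the uncovered time is 0. The documents do not say which reading applies.

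**What the summary would contain:** a patient who crosses over at Month 3 has the next forms at original Months 3 + 6 = 9 and 3 + 12 = 15. On the literal reading both cover time after allograft. Because the mITT analysis is as randomised, both are reported under conservative care, while the first 3 months are absent. SAP 9.2 has no rule for separating the two periods, and the treatment-received analysis in SAP 11.1 is limited to the primary endpoints.

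**The case against.** Several counter-arguments carry weight.

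- **A reader might infer that resource use is never reviewed before crossover.** The documents do not support that. A patient who crosses over after the original Month 6 visit has already had a review back to original Day 0. Section 7.1.2 also names resource utilization among the Day 0 assessments, and the crossover visit is a new VA1. That section defers to Appendix A, which leaves VA1 unmarked, so the two conflict. Non-collection at crossover is therefore not proven, but no look-back to original Day 0 is stated either. The recall period may be defined on the case report forms, which are not among the documents.
- **Part of the information is recorded elsewhere.** Adverse events are recorded from Day 0 (8.5) and marked at Month 3 in Appendix A. Inpatient hospitalization is a seriousness criterion (14.2). Follow-up operations are documented separately (8.5), and hospitalization and re-operation are endpoints in their own right (SAP 3.2.2). Of the items named in 9.3, subsequent surgeries are largely covered. Days off work and other clinic visits are not.
- **A reader might infer that the conservative-care figure is understated.** This is plausible but not shown. Crossovers still supply two post-treatment reviews, so their window is shifted rather than shortened, and it is unknown whether use after injection is lower or higher than before it.
- **The consequence is limited.** The SAP plans only a descriptive summary, within secondary analyses that it calls exploratory.

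What remains is a real gap on the literal schedule and an ambiguity on every other reading. If sites choose different look-back dates, their forms cover different periods and cannot be pooled cleanly.

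**Conclusion.** The point holds for crossovers before the original Month 6 visit: on the literal schedule, about 2.5 to 7 months of conservative care have no scheduled resource-use review. For later crossovers, only the time since the Month 6 visit is uncovered. This assumes that Day 0 means the crossover visit and that no form is taken at VA3 or at the new VA1.

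The affected patients are selected largely for decline, though not entirely, since crossover is optional and can rest on physician discretion.

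The bias cannot be sized. A reader might compute the share of the arm's conservative-care time that goes unreviewed. With an assumed crossover fraction f, crossover at Month 3 and 12 months for everyone else, that share is 3f/[12(1 − f) + 3f]: 8%, 20% and 43% at f = 25%, 50% and 75%. These are shares of time under an assumed f. They are not a bias in any reported quantity, and the formula does not apply to crossovers after Month 6. The trial's success criterion is not affected. The change is worth making because it is cheap and because the lost information cannot be fully recovered later.

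**What to change.** - **Appendix A and Protocol 7.1.4:** add the existing Resource Utilization form at VA3 and at the crossover visit before injection, each covering the time since the last form or, if there is none, since original Day 0.
- **Protocol 7.1.5:** state which Day 0 the Month 6 look-back uses for crossovers.
- **Protocol 7.1.2 and Appendix A:** reconcile whether resource use is taken at Day 0.
- **SAP 9.2:** show conservative-care resource use before crossover, per month observed, separately from use after crossover.

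A fixed window of 12 months from original Day 0 is not recommended. After a Month 3 crossover the later visits fall near original Months 9 and 15, so the last form would have to be split or a visit added.

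The cost is a small questionnaire burden for at most 40 patients and slightly more analysis work. If the visits are already complete, the SAP change can still be made, with a statement of how many pre-crossover months were not observed.

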7.2 Appropriateness of measurements

The Oswestry low back pain disability questionnaire (according to Hudson-Cook) or OPDQ, a self-rating scale, will be used to calculate the Oswestry Disability Index (ODI), the primary efficacy criterion. The use of this scale in clinical trials is recommended for its acceptable test quality and satisfactory test-retest reliability.

A composite primary endpoint with the ODI as well as a pain score (VASPI) will be used to increase the efficiency of this small trial.

Additionally, the SF-36, an often-used scale to assess patients' general condition and quality of life, and the visual analogue scale of pain intensity (VASPI), a standard to measure general pain are used as secondary criteria.

CONFIDENTIAL	Clinical Protocol	DATE	Р	age
		9Dec2019		
	mented Disc Regeneration in the T reatment of the or without Intervertebral Disc Herniation –	WRITER TG, DB, PW	NO. 32	REV 6

Therefore, a number of measurements are used to assess the clinically relevant symptoms in intervertebral disc pain as well as functional disability. Additionally, morphological changes will be observed by MRI and X-ray.

7.2.1 Primary efficacy variable

The reduction of back pain attributable to lumbar disc degeneration, assessed by the outcomes of the ODI and VASPI questionnaires, that will be determined for the primary efficacy variable at 6 and 12 months after treatment.

7.2.2 Secondary efficacy variables

Analogous to the primary parameter, the rates concerning the other recorded scores, and the ODI at other time points, with different definitions of healing will be analyzed as well.

MRI will be evaluated with respect to intervertebral height, disc desiccation, adjacent vertebral endplate morphology and Pfirmann grading score.

An assessment of the tissue repair by X-ray and MRI will be performed by a panel of physicians blinded to treatment.

CONFIDENTIAL	Clinical Protocol	DATE	P	age
		9Dec2019		
	mented Disc Regeneration in the T reatment of the or without Intervertebral Disc Herniation –	WRITER TG, DB, PW	NO. 33	REV 6

8 INCLUSION / EXCLUSION CRITERIA

8.1 Inclusion Criteria

Patients will be entered into this study only if they meet ALL of the following criteria:

- Able to provide an English written Informed Consent
- Age 18 to 60 years inclusive
- Male or female
- Body mass index <35
- Pfirrmann Grade [3-6]
- Radiographic confirmation by MRI/X-ray of:
 - (1) translational instability defined as ≤5 mm, or
 - (2) angular instability defined as ≤5°
- Back pain (with or without radicular leg pain) measured by:
 - (3) ODI of at least 40%, and
 - (4) VASPI of at least 40mm
- Pathologic level between L1 and S1
- 1 or 2 vertebral level involvement that has been evaluated for at least 6 months and treated with conservative care
- Symptomatic back pain attributable to intervertebral disc for a minimum of 6 months
- No previous surgical treatment at the disc level(s) being considered
- Psychosocially, mentally and physically able to fully comply with this protocol, and follow-up schedule
- Ability to undergo allograft transplantation
- Life expectancy >2 years
- No contraindications to MRI
- No history of malignancy (basal cell carcinoma) or chronic infectious disease (e.g. HIV, Hepatitis)
- Agree to use appropriate contraception; not planning on becoming pregnant for 24 months after treatment
- Patient disc for transplant confirmed by inter-discal pressure measurement, or disc-imaging study.
- No signs or symptoms of infection
- No chronic use (>7 consecutive days) of anticoagulants (such as aspirin) or NSAIDs prior to treatment

CONFIDENTIAL	Clinical Protocol	DATE	P	age
		9Dec2019		
	mented Disc Regeneration in the $\underline{\mathbf{T}}$ reatment of th or without Intervertebral Disc Herniation –	WRITER TG, DB, PW	NO. 34	REV 6

8.2 Exclusion criteria:

- Seropositive or seronegative spondyloarthropathy
- Type III Modic changes
- Prior surgeries of segments between L1 and S1
- Chemonucleolysis or percutaneous laserectomy of the affected disc prior to the study
- Chronic facet syndrome
- Stenosis of the spinal canal that is moderate to severe or more in degree
- Spondylodiscitis
- Spondylolisthesis (lysis and degenerative)
- Severe motor deficit or cauda equina disorder based on investigator determination
- Congenital abnormalities of the spinal nerves
- Pelvic and inguinal angiopathy
- Neurogenic inguinal syndrome
- Syringomyelia
- Diastenomatomyelia
- Traumatic neurological disorders
- Diseases of the kidney (nephritis, pyelonephritis)
- Other severe diseases of any other major body system as judged by the investigator
- Regular intake of systemic steroids
- Malignant diseases of any solid organ or any hematologic malignancy during the previous 5 years
- Patients who have participated in a clinical trial within the last month prior to inclusion
- Moderate to severe or greater lumbar stenosis of both transplantation endplates and adjacent levels

CONFIDENTIAL	Clinical Protocol	DATE	Р	age
		9Dec2019		
	mented Disc Regeneration in the $\underline{\mathbf{T}}$ reatment of th or without Intervertebral Disc Herniation –	WRITER TG, DB, PW	NO. 35	REV 6

MATERIALS AND METHODS

8.3 Test Material

The material used for this study will be a proprietary supplemental cellular allograft nucleus pulposus obtained from donors at UMTB. The tissue will be processed using UMTB SOP and provided to participating clinical sites for transplantation.

8.4 Study Procedure

On Day 0 of the Active Phase, eligible subjects will undergo transplantation of supplemental allograft, or saline (placebo), or continue active standard of conservative care. This conservative care procedure will not be defined by this protocol however standard practice is to be followed by each physician. All subjects who undergo successful treatment will continue in the study and be followed as per the standard of care. Subjects randomized to continuing conservative care will be assessed at 3 months, and clinical indices will be assessed. These conservative care subjects who have experienced a significant decline in condition defined as a 10% increase in pain by VASPI, or a 9-point increase in ODI will be offered the allograft as a crossover. If the subject does not meet the aforementioned changes in ODI or VASPI, or is considering withdrawal, they may be offered the allograft treatment by physician discretion if condition has significantly declined.

